## Treatment

- List the clinical dosage/dosage form, route, and dose regimen:

This section is not applicable since the proposed investigation does not involve medication dosing or include animals.

## Collateral Research

- Include biomarkers, PK, etc.

Not applicable.

## Statistical Plans

- Include justification for clinical sample size and primary hypothesis testing:

As noted above, our main dependent variables of interest will include: (1) mean reaction time per trial for each test; (2) # of correct responses per trial for each test; (3) # of errors of commission per trial for each test; (4) # of errors of omission per trial for each test; and (5) total # of errors per trial for each test. We will use these data to test Hypotheses 1-2 and to address our exploratory Aim which will examine the relationship between various nocturnal sleep measures and daytime performance scores. Our hypotheses testing will be accomplished using a 2 (PI vs. NS) x 2 (simple vs. complex test)

# A

factorial analysis. Although our statistical model could also include "trials" as a factor, we have chosen to limit the complexity of our analyses by excluding this factor and using mean values of each of our performance measures across trials for each participant in our analyses. To further simplify our analyses we will compute mean values of our 5 dependent measures for the three simple tests and another set of mean values of these dependent measures for our three complex tests and use those composite means in all planned analyses.

Before conducting tests of the study hypotheses, we will conduct a number of preliminary 2 (PI vs. NS) x 2 (alert vs. sleepy) x 2 (simple vs. complex test) ANOVAs and cross tabs analyses to determine if the various "cells" of our study include participants who do not differ significantly in terms of their mean ages, years of education, gender compositions and racial/ethnic compositions. If study "cells" are found to differ significantly on any of these variables, those variables will be used as covariates in statistical models designed to test study hypotheses. If study cells do not differ in regard to these variables we will use unadjusted statistical models to test study hypotheses.

For study hypotheses 1 & 2, we will conduct 2 (PI vs. NS) x 2 (simple vs. complex test) MANOVAs/MANCOVAs analyses to test for statistical significance across the multiple performance measures derived from the neuro-cognitive test battery. If the MANCOVA/MANOVA shows significant results, univariate ANCOVAs/ANOVAs will be conducted to tests for similar significant effects for each individual performance measure (i.e., mean reaction time; within subject standard deviations for reaction time; error responses).

Hypothesis 1 will be tested via examination of the main effect of the *group factor* (PI vs. NS) in these analyses. Findings showing significantly slower and more variable reaction times, fewer correct responses and higher error rates in the hyperaroused PI group will support this hypothesis. Elimination of these statistical differences in repeat analyses that use hyperarousal scale scores as a covariate will confirm the role of hyperarousal in explaining the observed group differences.

Hypothesis 2 will be tested via examination of the interaction of the *group factor* (PI vs. NS) and *test difficulty factor* (simple vs. complex) in these analyses. This finding coupled with a posteriori comparisons showing that PI participants have significantly poorer performances than do NS only on the complex tasks will support this hypothesis. Again, elimination of these statistical differences in repeat analyses that use each participant's hyperarousal scale score as a covariate will confirm the role of hyperarousal in explaining the observed group differences on complex tasks.

Our Exploratory Aim will require us to derive a variety of measures from the PSGs conducted on the two nights preceding daytime testing. Following the AASM Scoring Manual guidelines we will score these PSG records and obtain measures of total sleep time, sleep onset latency, wake time after sleep onset, sleep efficiency, and percentages of stages N1, N2, N3, and R for each night. We also will de-artifact each night and then perform a Fast Fourier Transform and subsequent sleep EEG spectral analysis as per our previously published reports to derive NREM absolute and relative spectral power measures in the delta, theta, alpha, sigma, beta and gamma bandwidths. Once these measures are derived for each night, we will compute mean values of these measures for the two PSG nights and then enter those into multivariate regression analyses to determine which measures predict each of the five performance variables used as dependent measures. Those found to be predictive of performance indices will be entered as covariates in the above factorial analyses to determine if any such measures account for the anticipated relative deficits shown by the insomnia group vis a vis the normal group. Since we will anticipate group differences only on the 5 performance measures derived from the set of complex tests, we will plan to test our sleep measures as covariates only in one-way group comparisons using response latency, correct response rate, and error rate data acquired from the complex tests as dependent measures in these analyses. We, thus, will conduct and 5 ANCOVA analyses in which the sleep measures are tested as covariates with each of the 5 performance measures obtained from the complex reaction time tests.

In addition to these analyses, we will conduct simple bi-variate correlational analyses as well as multi-variate regression analyses to examine the association between the EEG measures and subjects' scores on the hyperarousal scale. In regression analyses hyperarousal scores will be predicted by the various measures derived from conventional and spectral scoring of the PSG records.

These analyses could provide important new information about the relationship between nighttime sleep and daytime performance. Specifically these analyses could help identify specific aspects of the macro and micro-architecture of sleep that are markers for sleep-disruptive hyperarousal and produce impairment in daytime neuro-cognitive performance. These sleep measures therefore could be considered important targets for insomnia therapies to address in optimizing the types of neuro-cognitive endpoints studied herein. Such findings would seem of great interest to Merck and other

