In our efforts to follow up on this latter work, we recently examined the error rates of alert and sleepy PI sufferers and normal sleepers across a series of simple and complex reaction time tasks. We employed age and gender matched samples of PI (N=89) sufferers and normal sleepers-NS (N=95). Participants underwent three nights of PSG followed by daytime testing with a four-trial Multiple Sleep Latency Test-MSLT. The PI and NS groups were each subdivided into "alert" (e.g., MSLT mean onset latency > 8 minutes) and "sleepy" (e.g., MSLT mean onset latency  $\leq$  8 minutes) subgroups to allow for testing the main and interaction effects of participant type and level of alertness. "Alert" participants had longer MSLT latencies than "sleepy" participants (12.7 vs. 5.4 minutes). PI sufferers had fewer correct responses on performance testing than did NS. However, as shown by the adjacent, figure we found a significant group x alertness interaction ( $p = .0013$ ) with greater error rates occurring among alert (hyperaroused) PI sufferers (Mean=4.5 $\pm$ 3.6 errors per trial) than among alert NS (Mean=2.6 $\pm$ 1.9 errors per trial). This was particularly true for the more complex switching attention task.

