Our work along with that of Fernandez-Mendoza serve to confirm that PI sufferers have measurable objective neuro-cognitive deficits and provide some preliminary suggestion for the types of testing approaches that should be used to detect them. The identification of tests sensitive to PI sufferers' cognitive deficits are particularly relevant for testing the effects of current and future insomnia therapies on patients' objective daytime functioning. Measures of daytime dysfunction can and should serve as endpoints for assessing benefits and detriments of insomnia therapies. In addition, our recent work suggests that subgroups of PI sufferers may differ in their daytime deficits, with those showing physiological hyperarousal being most prone to make errors. This finding suggests that different types or doses of treatment may be needed to reverse the daytime impairments of the hyperaroused and non-aroused PI patients. However, our line of research would benefit by replication and extension findings to (1) further confirm the detrimental effects of physiological hyperarousal on PI sufferer's neuro-cognitive functioning; and (2) identify a broader range of tests that can be used for assessing diurnal cognitive impairments in both physiologically hyperaroused and lesser aroused PI groups. The current project will address these aims.

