# A

## Objectives

- List the objectives to correspond directly with the listed hypotheses:

**Aim 1:** To compare the performances of hyperaroused PI sufferers and normally alert normal sleepers across a battery of computer-administered neuro-cognitive reaction time tests.

**Aim 2:** To examine the relative sensitivities of a range of simple and complex reaction time tests for discriminating PI sufferers from non-complaining normal sleepers.

**Aim 3 (Exploratory):** To examine the degree to which measures of the macro- and micro-architecture of sleep account for the daytime performance deficits shown by hyperaroused PI sufferers

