## Hypothesis

- List the clinical Hypotheses in order of priority:

**Hypothesis 1:** Hyperaroused PI sufferers will show greater performance deficits (slower reaction times; fewer correct responses and more error responses) across repeated daytime testing trials than will age- and gender-matched normal sleepers.

**Hypothesis 2:** Complex reaction time tasks that require executive function, ability to switch attention, and higher order memory function will show greater discrimination of hyperaroused PI sufferers and normal sleepers on measures of mean reaction time, correct response rates and error rates than will simple reaction time tasks.

**Exploratory Aim 3:** To determine the possible sleep deficiencies/mechanisms that contribute to the relative daytime deficits in the hyperaroused PI subgroups we will test measures of sleep continuity (sleep and wake time) and the macro-architecture (sleep stage percentages) and micro-architecture (NREM sleep EEG spectral measures) derived from PSG on nights preceding daytime testing as covariates in study analyses to determine the degree to which they account for observed group differences.

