# A

administered battery of reaction time tasks. The assessment protocol will start two to three hours after participants' respective morning rising times and will begin with a battery of the neuro-cognitive testing followed by an MSLT nap. Per standard MSLT procedures, the daytime testing will be scheduled so the four performance testing and sleepiness assessment trials occur two hours apart. All daytime testing will be conducted under the supervision of trained laboratory technologists. Immediately prior to initiating daytime testing, participants' electrodes worn for the previous night's PSG will be checked and readjusted if necessary. Participants will be supervised between trials to prevent unscheduled sleep episodes. PSG electrodes will be worn for the entire day of laboratory testing and will not be removed until after the final trial is completed. Once the fourth performance/MSLT trial is completed and electrodes are removed, the participant will be allowed to leave the laboratory.

The neuro-cognitive test battery will include a 38 minute battery of simple and complex tests selected from CANTAB® Tests made available from Cambridge Cognition. The simple and complex tests will be presented in alternating order to control for the effects of fatigue on subjects' test performances. Among the simple tasks will be the Simple Reaction Time Test, Big Circle/Little Circle Test and Choice Reaction Time Test. These tests all provide measures of reaction time and motor speed but involve minimal cognitive load. The more complex tests will include the Rapid Visual Information Processing Test, The Spatial Working Memory Test and the Attention Switching Test. These latter tests collectively assess reaction time, attention, concentration, memory, and executive function, and thus, involve more cognitive load making them more sensitive to the deficits PI patients manifest. Both the simple and complex tests provide measures of respondents' mean reaction times, variability in reaction times across stimulus presentations, counts of correct responses, and counts of errors of omission and commission. These data are provided for each respondent for each trial allowing for analyses of respondents performances on a trial x trial basis as well as their average performances across trials.

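### Aim 2 asks about the sensitivity of a range of tests, but every planned analysis uses one simple and one complex composite, so none shows how well any single test separates PI from NS

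*Combined protocol and SAP*

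**What the plan says.** The Objectives section words Aim 2 as "To examine the relative sensitivities of a range of simple and complex reaction time tests for discriminating PI sufferers from non-complaining normal sleepers". Background and Rationale gives a reason for asking: the work should "identify a broader range of tests that can be used for assessing diurnal cognitive impairments", and measures of daytime dysfunction are proposed there as endpoints for insomnia therapies.

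Study Design/Clinical Plan names three simple tests (Simple Reaction Time, Big Circle/Little Circle, Choice Reaction Time). It continues: "The more complex tests will include the Rapid Visual Information Processing Test, The Spatial Working Memory Test and the Attention Switching Test". Data are available for each respondent and trial. Statistical Plans opens at the level of the single test: "our main dependent variables of interest will include: (1) mean reaction time per trial for each test", followed by four count measures, also defined for each test.

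The same section then averages over trials and over the tests within each class, giving one simple set and "another set of mean values of these dependent measures for our three complex tests and use those composite means in all planned analyses". Follow-up is by performance measure, not by test: "If the MANCOVA/MANOVA shows significant results, univariate ANCOVAs/ANOVAs will be conducted".

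Hypothesis 2 is worded by class of task: complex tasks "will show greater discrimination of hyperaroused PI sufferers and normal sleepers on measures of mean reaction time, correct response rates and error rates" than simple ones. Its support requires a group x difficulty interaction, together with follow-up contrasts in which PI do significantly worse only on the complex tasks. No rescaling of the composites is described.

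**The concern.** The measures are defined per test, but the word all in the composite sentence leaves no planned analysis at that level. A composite result says whether a class of three tests separates the groups. It does not say which test does so, and that is what someone choosing an endpoint for a treatment study needs to know.

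The plan's own background makes this more than formal. It reports a higher error rate in alert PI sufferers than in alert normal sleepers and adds: "This was particularly true for the more complex switching attention task". The battery has one test named for attention switching, and it is averaged with two others. If the deficit sits mainly there, averaging weakens it; if all three complex tests carry it, averaging strengthens it. The composite alone cannot tell these cases apart. Any per-test result reported later would be unplanned.

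A smaller point concerns scale. The planning SD for complex latency is twice that for simple latency, so a raw interaction in milliseconds is not by itself a comparison of separation relative to spread.

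**Working it through.** **Inputs from Power Considerations.** n = 82 per group, alpha = .05 (taken as two-sided, which fits the stated powers).
- Complex latency: 496.65 vs 438.14 ms, SD 133.4, difference 58.51.
- Simple latency: 247.9 vs 226.4 ms, SD 66.8, difference 21.5.

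**Assumed, not in the documents.** The three tests in a class have equal SDs and inter-test correlation r = .3 to .7. The simple-complex correlation is rho = .3 to .8.

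**1. The plan's own figures.** d = difference/SD.
- Complex: 58.51/133.4 = .439. Two-sample t power (noncentral t, 162 df) = .797; the plan states .80.
- Simple: 21.5/66.8 = .322. Power = .535 (.540 by the normal approximation); the plan states .54.

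Both reproduce, so the point does not rest on an arithmetic error.

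**2. What a composite does to a test with d = .439.** The mean of three unit-SD tests has SD = sqrt((1+2r)/3). Composite d = (mean of the three d values)/SD.

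| Other two complex tests | r = .3 (SD .730) | r = .5 (SD .816) | r = .7 (SD .894) |
|---|---|---|---|
| No difference | d .200, power .247 | d .179, power .207 | d .163, power .180 |
| Half the difference | d .400, power .722 | d .358, power .625 | d .327, power .548 |
| The same difference | d .601, power .969 | d .537, power .928 | d .490, power .877 |

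The test alone has power .80. The composite loses in the first two rows and gains in the third.

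**3. The reverse question.** A composite d of .439 fits three tests at d = .439 x SD = .320, .358 or .392 each. It fits equally well one test at 3 x .439 x SD = .96, 1.07 or 1.18 and two at zero. The composite cannot separate these.

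**4. Precision of per-test estimates.**
- One test: 1.96 x sqrt(2/82 + d^2/(4 x 82)) = .31 SD for d up to .44.
- Difference between two tests, both near d = .439: 1.96 x sqrt((2/82)(2-2r) + 2d^2(1-r^2)/(4 x 82)) = .368, .312 and .242 for r = .3, .5 and .7.
- Count: 6 tests x 5 measures = 30 intervals at most; 30 x .05 = 1.5 expected to exclude zero if nothing differed.

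**5. Scale in Hypothesis 2 (latency).**
- Planned raw interaction: 58.51 - 21.5 = 37.0 ms.
- Ratio of raw differences: 58.51/21.5 = 2.7. Ratio of d: .439/.322 = 1.36.
- Equal d in both classes would still give .322 x (133.4 - 66.8) = 21.4 ms, or .439 x 66.6 = 29.2 ms.
- Standardised difference between classes: .439 - .322 = .117 SD. At rho = .3, .5, .7 and .8 its power is .10, .12, .16 and .22, and its CI half-width is .37, .31, .24 and .20 SD.
- Simulation of the full Hypothesis 2 rule under equal d (significant interaction, significant complex contrast, non-significant simple contrast), without the multivariate gate: the rule is met about 5-11% of the time.

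**The case against.** The strongest reply is that the objectives are meant to correspond to the hypotheses. Aim 2 can then be read as the class contrast of Hypothesis 2, which the two-composite interaction addresses. That reading is fair. A reader might infer that the trial would end with no planned answer to Aim 2; the documents do not support going that far. What is missing is the answer at the level of the single test, which Aim 2's reference to a range of tests and the stated wish to identify usable tests both point to.

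Second, the composite is a deliberate simplification that limits multiplicity, and it need not cost power. A reader might infer from the switching-task background that averaging must dilute the effect. The third row of the table shows otherwise, and the plan expects its complex tests collectively to be sensitive. The documents give no per-test effects, SDs or correlations, and do not say whether the .439 comes from one task or several.

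Third, per-test intervals cannot rank six tests well. This stands: half-widths of .24-.37 SD for a difference between tests are wide. They would still describe each test, which nothing planned now does.

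Fourth, on scale, a reader might infer that the Hypothesis 2 rule is badly miscalibrated. The figures do not show that. The requirement for significance only on the complex tasks holds false support to about 5-11%, and the multivariate gate limits it further. Greater discrimination is not defined in the documents, raw units are inferred because no rescaling is described, and the SD ratio comes from earlier data. Significance in one class and not the other is still not an estimate of a difference in discrimination, but this merits a reporting note and no more. Making support depend on a standardised interaction with power .10-.22 would be a poor trade.

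**Conclusion.** The point holds as a gap in the analysis plan; the data to be collected are sufficient. That no planned analysis is at test level follows from the plan's wording and needs no assumption. How much this matters depends on how the effect is spread over the complex tests: composite power runs from .18 to .97 around the .80 of a single test with d=.439, given equal SDs and inter-test correlation .3-.7. The composite tests of Hypotheses 1 and 2 can stand as planned.

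The scale point is secondary. On the planning latencies, 21.4-29.2 of the planned 37.0 ms would arise under equal standardised effects, so the raw interaction should not be reported alone as evidence of greater discrimination.

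**What to change.** Keep the composite tests and the Hypothesis 2 decision rule. Amend Statistical Plans as follows.

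- **Aim 2.** For each of the six tests, on each planned measure, report the standardised PI-NS difference with its 95% CI. Label these as estimation without multiplicity control. State that differences between tests have half-widths of about .24-.37 SD (under the assumed correlations), so any ranking is rough. Rank no measure first: the pilot remark on switching attention concerns errors, and the plan's Hypothesis 1 figures give a larger effect for errors (1.86/3.45 = .54) than for latency (49.8/112.1 = .44).
- **Hypothesis 2, reporting note.** Beside the raw interaction, show the standardised effect for each class and their difference with a CI, as description and not as a condition for support. State that the planned difference of .117 SD has power of only about .10-.22.

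**Cost.** No new data, visits or participants, since every measure is already defined per test. There is a little more analysis and up to 30 intervals to read, about 1.5 of which would exclude zero by chance if nothing differed. The chance of meeting the Hypothesis 2 rule is unchanged.

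### The covariate rule does not say that covariates are crossed with test difficulty; entered as main effects only, they leave the Hypothesis 2 interaction estimate unadjusted

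*Combined protocol and SAP*

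**What the plan says.** All of this is in Statistical Plans unless noted.

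- **Data structure.** The plan averages over trials and will then "compute mean values of our 5 dependent measures for the three simple tests and another set of mean values of these dependent measures" for the three complex tests. Each person therefore has two composites per measure, and difficulty varies within person.
- **Model.** Hypotheses 1 and 2 use 2 x 2 (group by difficulty) "MANOVAs/MANCOVAs analyses to test for statistical significance across the multiple performance measures derived from the neuro-cognitive test battery", followed by univariate ANOVAs or ANCOVAs.
- **Covariate rule.** Cells are compared on "mean ages, years of education, gender compositions and racial/ethnic compositions". Where they differ significantly, "those variables will be used as covariates in statistical models designed to test study hypotheses".
- **Hypothesis 2.** "Hypothesis 2 will be tested via examination of the interaction of the" group and difficulty factors. Support also needs follow-up contrasts: "This finding coupled with a posteriori comparisons showing that PI participants have significantly poorer performances than do NS only on the complex tasks".
- **Repeat analysis.** If the differences disappear in "repeat analyses that use each participant's hyperarousal scale score as a covariate", the plan takes hyperarousal to be confirmed as the explanation.

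The plan does not say how the two composites per person are modelled. It neither names nor excludes a covariate-by-difficulty term.

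**The concern.** Age, education, gender, race/ethnicity and the hyperarousal score belong to the person. They are identical in that person's simple and complex rows. The Hypothesis 2 interaction is the group difference in complex minus simple, and anything added equally to both rows drops out of it.

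An additive covariate is a natural literal reading of the plan. It describes a factorial ANCOVA, and its preliminary balance check uses simple versus complex as a cell factor even though the same people occupy both levels. On that reading, a variable that affects complex tests more than simple ones, and that differs between groups, would go on confounding the interaction while the report called the result adjusted. The hyperarousal repeat analysis has the same weakness: the interaction estimate could not move, whatever part hyperarousal plays.

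**Working it through.** **Inputs.** From Power Considerations: complex latency 496.65 (PI) and 438.14 (NS), SD 133.4 ms; simple latency 247.9 and 226.4, SD 66.8 ms; 82 per group; alpha .05. Not in the documents and therefore assumed: correlation between composites 0.5, covariate slopes of 0 to 60 ms per covariate SD, imbalance of 0.3 and 0.5 SD.

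**1. The plan's own figures.** Two-sided, normal approximation, with √(2/82) = 0.1562:

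- Complex: difference 58.51; 58.51 / (133.4 × 0.1562) = 2.81; power Φ(2.81 − 1.96) = 0.80, as stated.
- Simple: difference 21.5; 21.5 / (66.8 × 0.1562) = 2.06; power Φ(2.06 − 1.96) = 0.54, as stated.
- Implied interaction: 58.51 − 21.5 = 37.01 ms.

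**2. Why a main effect cancels.** Let g be group, x the covariate and γ its single slope.

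- Simple: S = a + b·g + γ·x + error
- Complex: C = a + d + (b + θ)·g + γ·x + error
- Difference: C − S = d + θ·g + error

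The covariate is absent from the difference. With complete pairs, the estimate of θ is the group difference in mean C − S, with or without x. No assumed value enters this step.

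**3. What stays behind.** Let the true slopes be βs (simple) and βc (complex), and the group difference in x be Δ.

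- Bias in the interaction = Δ × (βc − βs), unadjusted and main-effect-only alike.
- The main-effect model fits one slope, (βs + βc)/2, so it shifts both contrasts by Δ × (βs + βc)/2.

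**4. Expected values for one assumed case** (βs = 0, βc = 40 ms per SD, Δ = 0.5 SD). Bias 0.5 × 40 = 20 ms; common shift 0.5 × 20 = 10 ms.

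| ms | True | Unadjusted | Main effect only | Crossed |
|---|---|---|---|---|
| Complex contrast | 58.51 | 78.51 | 68.51 | 58.51 |
| Simple contrast | 21.50 | 21.50 | 11.50 | 21.50 |
| Interaction | 37.01 | 57.01 | 57.01 | 37.01 |

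Here the main-effect covariate half-corrects the complex contrast, wrongly shrinks the simple one and leaves the interaction untouched. That favours the complex-only pattern that the plan counts as support.

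**5. Simulation** (2,000 trials per row, 82 per group; mean interaction in ms, true value 37.01).

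| Slopes simple/complex | Imbalance (SD) | Unadjusted | Main effect only | Crossed |
|---|---|---|---|---|
| 20/20 | 0.3 | 37.41 | 37.41 | 37.27 |
| 20/20 | 0.5 | 36.39 | 36.39 | 36.37 |
| 0/20 | 0.3 | 42.59 | 42.59 | 36.55 |
| 0/40 | 0.5 | 57.00 | 57.00 | 36.84 |
| 20/60 | 0.5 | 57.57 | 57.57 | 37.37 |

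Unadjusted and main-effect-only estimates agreed to about 1e-12 in every trial. With equal slopes there was nothing to correct.

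**6. One simulated dataset** (slopes 5/40, imbalance 0.5 SD, mixed model). The interaction was 42.27 ms (SE 17.48, p = 0.0156) unadjusted and with the main effect, and 20.26 ms (SE 17.56, p = 0.25) when crossed. A single dataset does not measure bias. It shows that two readings of the same sentence can give opposite conclusions.

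**7. Hyperarousal score.** Study Design/Clinical Plan requires a score of at least 29 for PI and below 25 for NS. Entered as a main effect, the score falls under step 2. Crossed with difficulty, it can move the interaction, but no score is shared by both groups, so the adjusted group effect is an extrapolation.

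**The case against.** A reader might infer that covariate adjustment cannot affect Hypothesis 2 at all. The documents do not support that, for three reasons.

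- **The plan does not commit to main effects only.** If the two composites are treated as a multivariate or repeated-measures response, each has its own covariate slope and the covariate enters the equation for the difference. The named MANCOVA is open to that reading, under which the adjustment already works. This stands: the defect is an unstated choice.
- **Hypothesis 2 is more than the interaction.** It also needs the PI versus NS contrasts, and Power Considerations bases its Hypothesis 2 power on the complex-task difference. A main-effect covariate does move those contrasts. Likewise, the repeat-analysis sentence ends on complex tasks: "hyperarousal scale score as a covariate will confirm the role of hyperarousal in explaining the observed group differences on complex tasks". This stands too, but step 4 shows that the movement can be wrong when it comes from one averaged slope. A separate ANCOVA on each composite would avoid that for the contrasts, not for the interaction.
- **There are exceptions even with main effects only.** If pairing is ignored, the estimate is fixed but the SE and p move (20.95 to 20.53; .0445 to .0403 in the step 6 dataset). With some complex composites removed, the mixed-model estimate moves (27.8 to 32.3 ms).

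The size is also open to challenge. Slopes and imbalance are assumed, the rule applies only after a significant imbalance, and age and gender are matched by design, so education and race/ethnicity are the likelier triggers. That limits how often the problem would arise; it does not alter the algebra.

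**Conclusion.** The concern holds conditionally. If imbalanced person-level covariates enter the 2 x 2 model as main effects only and pairs are complete, the interaction estimate for Hypothesis 2 is exactly what it was without them. Any confounding from unequal slopes remains, and the complex and simple contrasts may be mis-corrected.

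The size is Δ × (βc − βs): zero for equal slopes, 6 ms (16% of 37.01) for 0.3 SD and a slope difference of 20, and 20 ms (54%) for 0.5 SD and 40. These are illustrations, not estimates for this trial. The documents do not show that an imbalance will occur, that slopes differ, or that the analyst would leave out the crossed term.

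For the hyperarousal repeat analysis, persistence of the interaction under a main-effect covariate says nothing about hyperarousal. Its elimination under a crossed covariate cannot confirm hyperarousal's role either, because group and score do not overlap.

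**What to change.** Add to Statistical Plans that, for Hypothesis 2, the simple and complex composites are analysed as repeated measures within person, and that each demographic covariate used (age, education, gender, race/ethnicity) enters together with its interaction with difficulty. Equivalently, run the ANCOVA on each person's complex-minus-simple score, with group and the covariates as predictors. Take the complex and simple contrasts from the same crossed model.

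The cost is one degree of freedom per covariate term among 164 participants; race/ethnicity may need several terms. In the step 6 dataset the SE rose only from 17.48 to 17.56.

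For the hyperarousal repeat analysis, do not interpret persistence of the interaction under a main-effect covariate. If the score is crossed with difficulty, report that the groups do not overlap on it by selection (at least 29 versus below 25), call the adjusted group effect an extrapolation, and drop the statement that elimination confirms the role of hyperarousal. The cost here is a weaker claim; an extra degree of freedom does not buy back the missing overlap.
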